9.4.5 BASELINE DESCRIPTIVE STATISTICS

Baseline data will be presented by treatment group and total. Data include stratification variables (clinic) demographics, liver enzymes, lipids, hematology, chemistries, metabolic factors, concomitant medications, comorbidities, and liver histology findings. P-values will be presented as descriptive statistics noting that any treatment group differences are due to chance.

9.4.6 PLANNED INTERIM ANALYSES

There are no planned interim analyses.

9.4.7 SUB-GROUP ANALYSES

There are no formal planned sub-group analyses. Exploratory sub-group analyses will include treatment effects of primary and selected secondary endpoints by stratum variable (clinic), demographics (age, race, sex), severity of NAFLD, and study drug adherence.

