6.4 STUDY INTERVENTION COMPLIANCE

Two important goals of this protocol are to optimize adherence to the pharmacological regimen and to maximize the retention of participants in the study. Assessment of adherence to the assigned study drug will provide clinic staff a means to identify participants having problems with adherence. Adherence will be assessed during the trial by conducting a brief, structured interview, in which the study coordinator will assist the patients in identifying problems in taking the study drug and in estimating adherence to the prescribed medicine since their previous visit. These assessments will guide the consideration of strategies to improve adherence. Resources may be provided by clinics to remove barriers to participation such as child care,

transportation, and parking expenses. These resources can be provided as cash, transportation vouchers, or parking passes. An honorarium may be paid to participants in recognition of their time and effort when scheduled visits and procedures are completed successfully. Certificates of appreciation may be given at randomization and at conclusion of the VEDS trial as an incentive. Counts of capsules in the patient's returned blister packaging will be used as a measure of adherence at the end of the treatment period.

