7 STUDY INTERVENTION DISCONTINUATION AND PARTICIPANT DISCONTINUATION/WITHDRAWAL

7.1 DISCONTINUATION OF STUDY INTERVENTION

If the participant is in the treatment phase of the trial, and he/she develops a treatment related CTCAE v5.0-defined adverse event grade 3 or above, the medication will be stopped and the participant assessed by the site study investigator who is a licensed physician/hepatologist. If the adverse event was severe, prolonged, or in the view of the investigator the participant is intolerant of the medication, the study drug will be stopped and the participant will no longer receive the study medication, but will continue to be followed in the study according to the protocol, in keeping with the "intention-to-treat" paradigm.

Participants will be monitored for drug induced liver injury and will use the scale below to grade the adverse effects*:

	Grade 1	Grade 2	Grade 3	Grade 4
ALT	BSL elevated: 3x BSL or >400 U/L	BSL elevated: >3-5x BSL	BSL elevated: >5 -20x BSL	BSL elevated: >20x BSL
AST	BSL nl:3 x ULN BSL elevated: 3x BSL	BSL nl:>3-5 x ULN BSL elevated: >3-5x BSL	BSL nl:>5-20 x ULN BSL elevated: >5-20x BSL	BSL nl:>20 x ULN BSL elevated: >20x BSL
Total Bilirubin	1.5 x ULN	>1.5-3.0 x ULN	>3.0-10.0 x ULN	>10.0 x ULN

Any participant found to meet the above criteria for grade 2 or higher drug induced liver injury will have the study medication stopped pending further study investigator evaluation.

In addition, participants will have the study medication stopped if **ANY** of the following occur[81]:

If normal baseline AST:

- AST value $>5 \times \text{ULN}$ in two repeat tests (within 14 days); OR
- AST value is $>8 \times \text{ULN}$; **OR**
- AST value $>5 \times \text{ULN}$ AND total bilirubin $>2 \times \text{ULN}^\ddagger$ OR presence of symptoms suggesting liver injury (severe fatigue, nausea, vomiting or right upper quadrant pain),

If elevated baseline AST or ALT:

- ALT or AST value $>3 \times \text{BSL}$ or 300 U/L in two repeat tests (within 14 days); OR
- ALT or AST value $>5 \times \text{BSL}$ or $>500 \text{ U/L}$ (whichever occurs first); OR
- ALT or AST value $>3 \times \text{BSL}$ or $>300 \text{ U/L}$ (whichever occurs first) AND total bilirubin $>2 \times \text{ULN}^\ddagger$ OR presence of symptoms suggesting liver injury (severe fatigue, nausea, vomiting, or right upper quadrant pain)

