Follow-up visits will continue, but the study medication will not be restarted. The participant will be included in intention-to-treat analyses.

Additionally, if a participant is found to have signs of increased bleeding (i.e. petechiae) on physician assessment or a participant reports any signs of increased bleeding (i.e. bleeding gums), the study medication will be discontinued until the participant can be further examined by a study physician. The study medication may be restarted after further examination if the bleeding was not associated with a serious adverse event (CTCAE grade 3 or higher) and if the study physician deems a re-challenge appropriate.

* Values for ULN are defined at each clinical center per laboratory guidelines.

‡ For participants with suspected Gilbert's Syndrome at baseline: doubling of direct bilirubin

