9.3 POPULATIONS FOR ANALYSES

The analysis dataset will include:

- Intention-to-Treat (ITT) Analysis Dataset (i.e., all randomized participants)
- Safety Analysis Dataset: defines the subset of participants for whom safety analyses will be conducted (e.g., participants who took at least one dose of study intervention)
- Other Datasets that may be used for sensitivity analyses (e.g. subgroups by dose, sex, age, baseline labs, adherence)

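### Section 9.4.7 plans exploratory treatment effects by study-drug adherence, a post-randomization variable, so those contrasts are not protected by randomization and can be biased

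*Combined protocol and SAP*

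**What the plan says.** Section 9.4.7 opens with "There are no formal planned sub-group analyses". It then says that exploratory ones will estimate treatment effects on the primary endpoint and selected secondary endpoints by clinic and by "demographics (age, race, sex), severity of NAFLD, and study drug adherence". Section 9.3 allows further datasets for sensitivity analyses, with the examples "subgroups by dose, sex, age, baseline labs, adherence".

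Section 6.4 describes two adherence measures. One is a structured interview covering the time since the previous visit; the schedule in section 1.3 places adherence review at weeks 4, 8, 12 and 24. The other is a capsule count, which "will be used as a measure of adherence at the end of the treatment period".

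Section 7.1 ties exposure to liver tests. Participants meeting "grade 2 or higher drug induced liver injury will have the study medication stopped", pending evaluation. After the further list of ALT, AST and bilirubin criteria it states: "Follow-up visits will continue, but the study medication will not be restarted". Bleeding signs interrupt drug, with restart possible, and related events of grade 3 or above stop it. Section 7.2 lets the investigator withdraw a participant for non-compliance.

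The primary analysis is intention-to-treat (9.2, 9.4.1, 9.4.2), and section 7.1 keeps participants stopped for liver tests in it.

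**The concern.** Adherence is listed beside baseline factors as if it were one. A subgroup fixed at baseline keeps the randomized comparison inside each stratum. A subgroup formed by what happened during treatment does not, if what puts a person in the stratum differs by arm. Here it can: tolerability and bleeding may vary with dose, and a rise in the endpoint analyte itself can end treatment. Adherers on vitamin E and adherers on placebo may then differ in prognosis.

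The documents give no adherence cut-off, no rule for counting protocol-mandated stops, no causal method and no caveat. In a dose-finding trial, a table of adherers by dose is likely to be read as what each dose does when taken, and these contrasts do not estimate that.

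**Working it through.** The documents state no figure for the adherence subgroups, so there is none to reproduce.

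**Inputs from section 9.2:** planned difference 20 percentage points, SD 31, 50 per arm, 10% missing, so 50 × 0.90 = 45 evaluable per arm. All else is assumed. A positive difference means a larger ALT fall on vitamin E. In every scenario the drug effect is the same for everyone whatever they take, so any departure from the true value is selection alone.

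**1. Adherence rates differ by arm (closed form).** Adherence is a normal latent variable with correlation r to a prognostic factor of SD s. The mean prognosis is r·s·φ(z)/p in adherers and −r·s·φ(z)/(1−p) in non-adherers, where p is the proportion adherent and z its normal quantile. Assumed: r·s from 0.5 × 9.3 = 4.65 to 0.8 × 15.5 = 12.4 points.
- 85% adherent on placebo, 70% on a dose. Adherers: 0.497 − 0.274 = 0.222, giving a bias of +1.0 to +2.8. Non-adherers: −1.159 + 1.554 = 0.395, giving +1.8 to +4.9.
- 90% against 60%. Adherers: 0.644 − 0.195 = 0.449, giving +2.1 to +5.6, so a true 20 is read as up to 25.6. Non-adherers: −0.966 + 1.755 = 0.789, giving +3.7 to +9.8.

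**2. Prognosis drives adherence differently by arm (simulation).** About 80% adherent; prognosis carries 60% of the outcome variance; log-odds of adherence 0.3 per SD of prognosis, plus or minus 0.7 in the vitamin E arm.

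| True difference | Interaction | Adherers | Non-adherers |
|---|---|---|---|
| 20 | +0.7 | 23.2 | 10.2 |
| 20 | −0.7 | 16.6 | 33.2 |
| 0 | +0.7 | +3.4 | −9.8 |
| 0 | −0.7 | −3.3 | +12.7 |

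In the second row adherence was 79.6% on placebo and 79.4% on vitamin E, so similar observed adherence does not rule bias out. As a control, when prognosis acted equally in both arms (0.7 per SD), a true 20 stayed at 20.0 in both strata. Bias needs selection that differs by arm.

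**3. ALT-type stopping alone (simulation).** 85% otherwise adherent; stopped if the interim value falls in the worst tail; correlation of interim and week-24 values 0.4 to 0.8; true difference 20.

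| Placebo stopped | Vitamin E stopped | Adherers | Non-adherers |
|---|---|---|---|
| 1% | about 0.15% | 19.79 to 19.48 | 21.51 to 23.08 |
| 5% | 1.1% | 19.05 to 18.05 | 24.02 to 27.44 |
| 10% | 2.7% | 18.40 to 16.75 | 24.10 to 28.04 |
| 20% | 6.9% | 17.46 to 14.87 | 22.43 to 25.06 |

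The sign follows from the mechanism: when the drug works, more placebo participants with a poor course are stopped, so the remaining placebo adherers look better. With a true difference of 0, every result lay within 0.2 of zero.

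A more literal check used one time point, thresholds of 3 times baseline or 300 U/L, and an assumed lognormal baseline ALT (median 90 U/L before truncation to 60–400). It stopped about 0.3% on placebo and 0.1% on vitamin E, and gave 20.0 in adherers and 20.2 in non-adherers.

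**4. Precision.** With 85% and 70% adherent, non-adherers number 45 × 0.15 ≈ 7 and 45 × 0.30 ≈ 14. The 95% half-width is 1.96 × 31 × √(1/7 + 1/14) = 28 points.

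**The case against.** The strongest defence is status. Section 9.4.7 disclaims formal subgroup analyses, section 9.3 only permits the adherence datasets, and nothing confirmatory uses them. That stands, and it limits the weight of the point. It does not answer it: an exploratory label warns about multiplicity and strength of evidence, but does not make the arms within a stratum comparable.

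The second defence is that the liver-test route is thin, since the thresholds are high, the grade 2 stop is pending evaluation and bleeding holds can be lifted. This also stands in large part. The 14.87 result needs an assumed 20% of placebo participants stopped. The documents give no baseline ALT distribution, however, and entry allows ALT up to 400 U/L while some stopping criteria name 300 U/L, so the true rate is unknown.

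Third, it might be said that participants lost early have no adherence value. That is not so: someone lost after week 8 has interview data and lacks the week-24 ALT instead.

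Finally, a two-stage least-squares model on mean mg/day may look like the natural replacement. It forces a straight line through dose. Take full adherence, equal arms and true effects of 20, 20 and 20 at 133.4, 266.8 and 533.6 mg. In units of 133.4 mg the doses are 0, 1, 2, 4 (mean 1.75) and the effects 0, 20, 20, 20 (mean 15). The slope is (140 − 4 × 1.75 × 15)/(21 − 4 × 1.75²) = 35/8.75 = 4, implying effects of 4, 8 and 16. The lowest dose is understated by 16 points, although the Williams' test described in section 9.2 allows a plateau.

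**Conclusion.** The point holds as a defect in a planned exploratory analysis. Treatment effects within adherence strata are not protected by randomization and can be biased, by a few points in adherers and by more in non-adherers under the scenarios above, against a planned effect of 20. Those figures rest on assumed adherence rates, correlations and stopping rates, and they illustrate the range without predicting it. The net direction is unknown because the routes can oppose each other.

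A reader might infer more than this, and the documents do not support it:
- That the estimates certainly are biased, or that the ALT rules are the main cause. Without rates, only the possibility can be shown.
- That the dose ordering would reverse among adherers. No calculation across the three doses supports that.
- That the trial's main conclusion is at risk. The minimum effective dose is decided in the intention-to-treat dataset, without reference to adherence.

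**What to change.** Remove adherence from the subgroup list in 9.4.7 and from the dataset examples in 9.3. Add that adherence will be summarised by assigned arm, that protocol-mandated stops will be shown separately, and that no treatment effect will be estimated within adherence strata.

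If an effect when taken is wanted, pre-specify one separate exploratory estimate for each dose against placebo, in all randomized participants, with assigned arm as instrument:

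complier effect = (mean endpoint on dose − mean endpoint on placebo) / (proportion adherent on that dose).

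Define adherent in advance, using capsule counts supplemented by the interview data. Use the missing-data approach of the primary endpoint: complete cases up to 10% missing, multiple imputation above that. Do not fit a linear per-mg model.

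The cost is SAP wording and, if the option is taken, three pairwise estimates on data already collected. Sample size, primary analysis and clinical rules do not change. The estimate assumes that assignment affects ALT only through being adherent as defined, which partial takers below the cut-off would strain. Its interval is also wider. The intention-to-treat half-width is about 1.96 × 31 × √(2/45) = 12.8 points; at an assumed 70% adherence it becomes roughly 12.8/0.70 = 18.3, treating that proportion as known.

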9.4.8 TABULATION OF INDIVIDUAL PARTICIPANT DATA

For monitoring of adverse effects, individual data may be presented to the Data and Safety Monitoring Board. In that case, study patients will be identified only by study ID. Names and other unique individual identifiers such as Social Security Number are not collected by the study and therefore will not be presented to the DSMB. Data on individual patients will not be presented in any manuscript or presentation.

9.4.9 EXPLORATORY ANALYSES

In parallel to the ANCOVA statistical methods used to compare continuous endpoints between the treatment groups for both the primary and secondary endpoints, we will compare results arising from ANOVA analysis (linear regression of 24-week change among treatment groups without adjusting for the baseline value of the continuous endpoint) will be used for exploratory analyses. Since ANCOVA and ANOVA are alternative models for “difference in difference” data as in the VEDS trial, we expect, given the randomized design, that the two methods will give similar results for the primary and secondary endpoints.

10 SUPPORTING DOCUMENTATION AND OPERATIONAL CONSIDERATIONS

10.1 REGULATORY, ETHICAL, AND STUDY OVERSIGHT CONSIDERATIONS

10.1.1 INFORMED CONSENT PROCESS

10.1.1.1 CONSENT AND OTHER INFORMATIONAL DOCUMENTS PROVIDED TO PARTICIPANTS

Consent forms describing in detail the study intervention, study procedures, and risks are given to the patient and written documentation of informed consent is required prior to participation in the study.

Master consent documents will be approved by the single Institutional Review Board of reliance (sIRB) for the study for screening to determine eligibility with an affirmation of consent for enrollment in the study. Relying sites may not delete material from the master consent. Relying sites will add a site-specific addendum containing locally required language to the master consent. The consent document will describe the purpose of the study, the procedures to be followed, and the risks and benefits of participation. Copies of the signed consent forms will be provided to the patient by paper or electronically, and this fact will be documented in the patient’s record.

At relying sites in which Spanish-speaking patients will be recruited, certified translations of the consent document will be available in Spanish.

10.1.1.2 CONSENT PROCEDURES AND DOCUMENTATION

Informed consent is a process that is initiated prior to the individual's agreeing to participate in the study and continues throughout the individual's study participation. Consent forms will be Institutional Review Board (IRB)-approved and the participant will be asked to read and review the document. The investigator will explain the research study to the participant and answer any questions that may arise. A verbal explanation will be provided in terms suited to the participant's comprehension of the purposes, procedures, and potential risks of the study and of their rights as research participants. Participants will have the opportunity to carefully review the written consent form and ask questions prior to signing. The participants should have the opportunity to discuss the study with their family or surrogates or think about it prior to agreeing to participate. The participant will sign the informed consent document prior to any procedures being done specifically for the study. Participants must be informed that participation is voluntary and that they may withdraw from the study at any time, without prejudice. A copy of the informed consent document will be given to the participants for their records. The informed consent process will be conducted and documented in the source document (including the date), and the form signed, before the participant undergoes any study-specific procedures. The rights and welfare of the participants will be protected by emphasizing to them that the quality of their medical care will not be adversely affected if they decline to participate in this study. This process may be completed in-person or remotely.

If the consent process is to be completed remotely WITHOUT an electronic signature, the following procedures must be followed:

- A copy of the sIRB approved Informed Consent document must be provided to the participant prior to the teleconsent meeting either via email, fax or mail or must have been previously provided during an in person visit. The person conducting the consent process may conduct the process via telephone or video conference.
- After the consent designee and participant reviews the consent form, the participant is offered the opportunity to ask any questions and have those questions answered.
- The participant will sign and date/time the informed consent document.
- The consent designee must verify the participant physically signed the consent document either by viewing via video conference, obtaining a photo of the complete signed consent document, or obtaining verbal confirmation from the participant that he/she signed the consent form and agreed to participate electronically.
- The signed document is then mailed, emailed or faxed to the consent designee.
- If the signed consent is emailed or faxed or returned via photo, the participant will be asked to return the original signed document on their first in person visit. Once received, the sIRB-approved consent designee signs, dates/times the original informed consent document. Both the original and emailed or faxed copy should be retained in the patient record and a copy of the original signed by both parties should be provided to the patient.
- If the informed consent form is mailed to the consent designee by the participant, the sIRB-approved consent designee will sign the copy which they possess after the participant has acknowledged signature on their copy. Once the original is received by the consent designee the copies will be attached to make a single document.

If electronic signatures are permitted per local institutional guidelines, an electronic documentation of the consent process is permissible.

10.1.2 STUDY DISCONTINUATION AND CLOSURE

This study may be temporarily suspended or prematurely terminated if there is sufficient reasonable cause. Written notification, documenting the reason for study suspension or termination, will be provided by the suspending or terminating party to study participants, investigator, funding agency, the Investigational New Drug (IND) sponsor and regulatory authorities. If the study is prematurely terminated or suspended, the Principal Investigator (PI) will promptly inform study participants, the reviewing single Institutional Review Board (sIRB), local IRB, and sponsor and will provide the reason(s) for the termination or suspension. Study participants will be contacted, as applicable, and be informed of changes to study visit schedule.

Circumstances that may warrant termination or suspension include, but are not limited to:

- Determination of unexpected, significant, or unacceptable risk to participants
- Demonstration of efficacy that would warrant stopping
- Insufficient compliance to protocol requirements
- Data that are not sufficiently complete and/or evaluable
- Determination that the primary endpoint has been met
- Determination of futility
- Cessation of in-person clinical activities due to a pandemic or other catastrophe

Study may resume once concerns about safety, protocol compliance, and data quality are addressed, and satisfy the sponsor, sIRB and/or Food and Drug Administration (FDA). The DCC will ensure that sites follow local, state, and institutional requirements regarding cessation and restart of Human Subjects research during the COVID19 pandemic or other natural disaster and collect IRB approvals, as indicated.

10.1.3 CONFIDENTIALITY AND PRIVACY

Participant confidentiality and privacy is strictly held in trust by the participating investigators, their staff, and the sponsor(s). This confidentiality is extended to cover testing of biological samples and genetic tests in addition to the clinical information relating to participants. Therefore, the study protocol, documentation, data, and all other information generated will be held in strict confidence. No information concerning the study or the data will be released to any unauthorized third party without prior written approval of the sponsor.

All research activities will be conducted in as private a setting as possible.

The study monitor, other authorized representatives of the sponsor, representatives of the single Institutional Review Board (sIRB), regulatory agencies or company supplying study product may inspect all documents and records required to be maintained by the investigator, including but not limited to, medical records (office, clinic, or hospital) and pharmacy records for the participants in this study. The clinical study site will permit access to such records.

The study participant's contact information will be securely stored at each clinical site for internal use during the study. At the end of the study, all records will continue to be kept in a secure location for as long a period as dictated by the reviewing sIRB, Institutional policies, or sponsor requirements.

Study participant research data, which is for purposes of statistical analysis and scientific reporting, will be transmitted to and stored at the NASH CRN Data Coordinating Center. This will not include the participant's contact or identifying information. Rather, individual participants and their research data will be identified by a

unique study identification number. The study data entry and study management systems used by clinical sites and by the NASH CRN Data Coordinating Center research staff will be secured and password protected. At the end of the study, all study databases will be de-identified and archived at the NASH CRN Data Coordinating Center and NIDDK Central Repository.

To further protect the privacy of study participants, the research is covered under a Certificate of Confidentiality by the National Institutes of Health (NIH). This certificate protects identifiable research information from forced disclosure. It allows the investigator and others who have access to research records to refuse to disclose identifying information on research participation in any civil, criminal, administrative, legislative, or other proceeding, whether at the federal, state, or local level. By protecting researchers and institutions from being compelled to disclose information that would identify research participants, Certificates of Confidentiality help achieve the research objectives and promote participation in studies by helping assure confidentiality and privacy to participants.

